4.6. Intracanalicular Depot Removal

For any subject, if at any point the intracanalicular depot is removed bilaterally by the Investigator for an adverse event, the subject will be exited from the study at the time of AE stabilization or resolution. If at any point for any subject the depot is removed bilaterally for subject discomfort, the subject will be exited from the study at that visit. If the intracanalicular depot needs to be removed from only one eye, the depot from the contralateral eye will not be removed and the subject will be followed per the study schedule for safety.

Once OTX-TP has been removed, the subject may be prescribed IOP-lowering drops for the affected eye(s) at the Investigator's discretion. Intracanalicular depots that are removed due to subject withdrawal or an undesired reaction at any point in the study will not be replaced.

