All subjects will undergo follow-up visits at 2, 4, 6, 8, 10, and 12 Weeks. If at any visit, the Investigator deems it necessary to initiate IOP-lowering drops as rescue therapy due to an increase in IOP, the subject will be considered an efficacy failure and will be followed through the remainder of the study for safety. If still present, the intracanalicular depot will not be removed. IOP measurements taken through the remainder of the study will be excluded from the efficacy analyses.

For any subject, if at any point the intracanalicular depot is removed bilaterally by the Investigator for an adverse event or subject discomfort, the subject will be exited from the study at that visit. If the intracanalicular depot needs to be removed from only one eye, the depot from the contralateral eye will not be removed and the subject will be followed per the study schedule for safety.

Intracanalicular depots that are removed due to subject withdrawal or an undesired reaction at any point in the study will not be replaced.

For subjects with Early Loss of Intracanalicular Depot Prior to the 6 Week Visit:

At any visit prior to the 6 Week Visit, if the intracanalicular depot is not visualized in one or both eyes by the Investigator, the Investigator will insert a new intracanalicular depot in the respective eye(s) after confirming patency. For any depot replacements, IOP assessments should be completed prior to replacement. The subject will continue to return for follow-up visits per the study schedule through the 12 Week Visit. The number of depot replacements will be tracked and documented on the appropriate electronic Case Report Form (eCRF).

For subjects with Early Loss of Intracanalicular depot from the 6 Week Visit prior to the 12 Week Visit:

At any visit from the 6 Week Visit prior to the 12 Week Visit, if the intracanalicular depot is not visualized in one or both eyes by the Investigator, the Investigator will insert a new intracanalicular depot in the respective eye(s) after confirming patency. For any depot replacements, IOP assessments should be completed prior to replacement. The subject will return for follow-up visits through the 12 Week Visit and then at the 20 Week Visit. Depots replaced between the 6 Week Visit and the 12 Week Visit will not be

removed at the 12 Week Visit. The first attempt to remove these depots will be at the 20 Week Visit. The number of depot replacements will be tracked and documented on the appropriate eCRF.

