Dosing compliance and treatment exposure will be assessed using visualization of the intracanalicular depot by the investigator, intracanalicular depot removal and the number of intracanalicular depots required in each eye for the 12 week period per subject. These analyses will be performed on the Safety Population. No statistical inference testing will be performed.

Intracanalicular Depot Visualization by the Investigator

The intracanalicular depot will be assessed for presence and ease of visualization at the time of insertion time point as well as the 8AM time point at each post-baseline visit. The number of subjects with a intracanalicular depot present will be summarized by visit and treatment, and this number will be used as the denominator for the ease of visualization responses. Ease of visualization will be recorded as Easy, Moderate, or Difficult by the investigator. Responses will be summarized by count and percentage at each visit by treatment group. A subject listing, reported separately by right and left eyes, will also be provided.

Intracanalicular Depot Removal

When an intracanalicular depot is removed the reason for removal (removed per protocol, AE, other), the success of the removal (yes vs no), the ease of removal (easy, moderate, difficult) and the method of removal (saline irrigation, application of manual pressure) will be recorded. The responses will be summarized by count and percentage at each visit by treatment group. A subject listing, reported separately by right and left eyes, will also be provided.

Number of Replacements

The number of intracanalicular depots required in each eye for the 12 week period per subject will be reported and listed. For subjects with confirmed depots beyond 12 weeks, summaries will also be provided indicating the length of the depot being present in the canaliculus and the number of depots required and the number of patency checks performed.

Treatment Exposure

Extent of treatment exposure for completed or discontinued subjects will be calculated in days using the following:

$$\text{Total Exposure (days)} = (\text{Date of last investigator visualization of a depot in either eye [that is not subsequently replaced]} - \text{Date of first insertion of a depot in either eye}) + 1$$

Date of first insertion of depot in either eye will in most cases be Baseline Visit 2 [Day 1]. Extent of treatment exposure for subjects who were lost to follow-up will be calculated in days using the following:

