Throughout the course of the study, all efforts will be made to remain alert to possible adverse events or untoward findings. If adverse events occur, the first concern will be the safety and welfare of the subject. Appropriate medical intervention will be undertaken. Any adverse events observed by the Investigator or reported by the subjects, whether or not ascribed to the study treatment, will be recorded on the subject's Adverse Event Case Report Form.

Documentation regarding the adverse event will be made as to the nature, date of onset, end date, severity, and relationship to study drug, action(s) taken, seriousness, and outcome of any sign or symptom observed by the physician or reported by the subject upon indirect questioning. All AEs will be coded using the MedDRA version 16.1.

AEs will be reported from the point subjects sign informed consent. The AE and treatment emergent adverse event (TEAE) reporting period ends upon study exit for new AEs. Existing AEs and TEAEs will be followed until:

- Resolution (return to baseline status or to 'normal')

- AEs may be determined to have resolved (completely) or resolved with sequelae.
- Principal Investigator determines, for events that do not end (i.e., metastasis), the condition to be chronic. The event can be determined to be resolved or resolved with sequelae.
- Stabilization of the event has occurred (no worsening expected by the investigator)

Adverse Event (or Adverse Experience, AE)

An AE is any untoward medical occurrence, which does not necessarily have to have a causal relationship with the treatment.

Adverse Ocular Event

An adverse ocular event is an AE that affects ocular tissues, the nasolacrimal duct, sinuses or vision. All adverse ocular events are a subset of adverse events.

Note: Subjects will be queried for the presence or absence of the following ocular complaints: excessive tearing, foreign body sensation, stinging/burning, and itching. Positive responses to these standardized ocular complaint inquiries should be reported as ocular complaints and not adverse ocular events unless the complaint: meets the criteria of a specific event as listed, and/or is: outside of normal limits, associated with clinical sequelae (e.g., adverse slit lamp examination findings), and requires an intervention to be resolved.

Treatment Emergent Adverse Ocular Event (or TEAOE)

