The expectedness of an AE should be determined based upon existing safety information about the study drug using these explanations:

- Unexpected: An AE or adverse reaction that is not listed in the study protocol, Investigator’s brochure, or prescribing information for the registered formulation of travoprost (Travatan®) or is not listed at the specificity or severity that has been observed.
- Expected: An AE that is listed in the Investigator’s brochure at the specificity and severity that has been observed.

AEs that are mentioned in the Investigator’s Brochure as occurring with a class of drugs or as anticipated from the pharmacological properties of the drug, but are not specifically mentioned as occurring with the particular drug under investigation are to be considered unexpected.

The Investigator should initially classify the expectedness of an adverse event, but the final classification is subject to the Medical Monitor’s determination.

AE Summaries

All AEs and TEAEs will be coded using MedDRA 20.0. AEs will be summarized in listings and tables for overall and ocular TEAEs by treatment group.

An overall summary will be presented that includes the number of AEs, TEAEs and the number and percentage of subjects who experienced at least one AE or TEAE, by treatment group and for all subjects. This summary will also include breakdowns of TEAEs further categorized as ocular (primary study eye and secondary study eye separately) or non-ocular, serious AEs (SAEs), ocular TEAEs by maximum severity, non-ocular TEAEs by maximum severity, related TEAEs, TEAEs leading to subject withdrawal, and deaths.

Additional summaries of TEAEs will be provided showing the number and percentage of subjects who experienced at least one TEAE and will be presented by SOC and PT. Non-ocular TEAEs will be summarized using discrete summary statistics and presented by treatment group at the subject and event level by SOC and PT. Ocular TEAEs will be similarly summarized at the subject level for both eyes and for primary study and secondary study eyes separately. If a subject reports the same PT multiple times within the same SOC, that PT will only be reported once within that SOC. As with the PT, if a subject reports multiple conditions within the same SOC, that SOC will only be reported once. In the summary, SOC will be listed in ascending alphabetical order; PTs will be listed in order of descending frequency for all subjects within each SOC.

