Table 14.2.1.8	Mean Observed, Change, and Percent Change from Baseline in Secondary Study Eye IOP by Time Point Observed Data Analysis	Full Analysis Set
Table 14.2.1.9	Mean Observed, Change, and Percent Change from Baseline in Secondary Study Eye IOP by Time Point Observed Data Analysis	Per Protocol Population
Table 14.2.2.1	Mean Observed, Change, and Percent Change from Baseline in Primary Study Eye IOP by Time Point and Strata MCMC Analysis	Full Analysis Set
Table 14.2.4.1	Insertion Results and Ease of Insertion	Safety Population
Table 14.2.4.2	Summary of Replacements	Safety Population
Table 14.2.4.3	Removal of Intracanalicular Depot	Safety Population
Table 14.2.5	Ocular Complaints by Study Eye	Safety Population
Table 14.2.6	Investigator Visualization of Intracanalicular Depot	Safety Population
Table 14.2.7	Punctum Examination Results	Safety Population
Table 14.3.1	Study Treatment Exposure	Safety Population
Table 14.3.2.1	Overall Summary of Adverse Events	Safety Population
Table 14.3.2.2.1	Non-Ocular Treatment Emergent Adverse Events by System Organ Class and Preferred Term	Safety Population
Table 14.3.2.2.2	Ocular Treatment Emergent Adverse Events by System Organ Class and Preferred Term	Safety Population
Table 14.3.2.2.3	Primary Study Eye Ocular Treatment Emergent Adverse Events by System Organ Class and Preferred Term	Safety Population

Table Number	Title	Population
Table 14.3.2.2.4	Secondary Study Eye Ocular Treatment Emergent Adverse Events by System Organ Class and Preferred Term	Safety Population
Table 14.3.2.2.5	Treatment Related Ocular Treatment Emergent Adverse Events by System Organ Class and Preferred Term	Safety Population
Table 14.3.2.2.6	Treatment Related Non-Ocular Treatment Emergent Adverse Events by System Organ Class and Preferred Term	Safety Population
Table 14.3.2.2.7	Serious Adverse Events by System Organ Class and Preferred Term	Safety Population
Table 14.3.2.2.8	Treatment Emergent Adverse Events Leading to Subject Withdrawal by System Organ Class and Preferred Term	Safety Population
Table 14.3.2.2.9	Ocular Treatment Emergent Adverse Events of Special Interest by System Organ Class and Preferred Term	Safety Population
Table 14.3.2.3	Treatment Emergent Adverse Events by System Organ Class, Preferred Term, and Maximum Severity	Safety Population
Table 14.3.2.4	Non-Related Treatment Emergent Adverse Events by System Organ Class, Preferred Term, and Most Likely Cause	Safety Population

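### Treatment is stopped per eye, but the AE outputs on stopping count only subject withdrawals, so no table shows which TEAEs led to depot removal

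*SAP*

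**What the plan says.** All SAP references are to Version 2.0.

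- **AE outputs on stopping.** AE Summaries (section 14) lists, among the breakdowns of TEAEs, "related TEAEs, TEAEs leading to subject withdrawal, and deaths". The planned table is 14.3.2.2.8, "Treatment Emergent Adverse Events Leading to Subject Withdrawal by System Organ Class and Preferred Term". Listings 16.2.8.3 and 16.2.8.6 give ocular and non-ocular events on the same basis.
- **Removal from one eye.** SAP section 4, General Study Design, says: "If the intracanalicular depot needs to be removed from only one eye, the depot from the contralateral eye will not be removed". The subject continues in scheduled safety follow-up. Protocol 4.6 has the same rule. Both say that a depot removed for an undesired reaction is not replaced.
- **Removal from both eyes.** SAP section 4 covers depots "removed bilaterally by the Investigator for an adverse event or subject discomfort, the subject will be exited from the study at that visit". Protocol 4.6 treats discomfort separately from an adverse event: when "the depot is removed bilaterally for subject discomfort, the subject will be exited from the study at that visit".
- **Complaints and AEs.** Under the Note in Protocol 5.1 and SAP section 14, tearing, foreign body sensation, stinging/burning and itching are ocular complaints by default. They become AEs if they meet a listed event, or if they are outside normal limits, "associated with clinical sequelae (e.g., adverse slit lamp examination findings), and requires an intervention to be resolved". For ocular hyperemia, discontinuation is itself an AE trigger (Protocol 5.5.1; SAP section 14).
- **Removal data.** The SAP subsection on depot removal records "the reason for removal (removed per protocol, AE, other"), summarised by count and percentage, by visit and arm (Table 14.2.4.3; Listing 16.2.5.4).

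**The concern.** Safety is part of the study objective, and the treatment is a device-like depot placed in each eye. Stopping for poor tolerability will often happen at the level of the eye. A table of events that led to stopping is where a safety reader looks for the reasons why treatment was not tolerated. Here that table is defined by the subject leaving the study, so it can omit an eye that lost its treatment because of an AE. It can also omit a subject who left because the depots were uncomfortable. Someone who reads the AE section alone would then understate intolerance, possibly in both arms, and could not see which events were responsible.

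**Working it through.** The plan states no figure on this point and no formula applies. The check is to follow each removal route through the exit rules, the AE definition and the planned outputs.

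| Route | Exit under Protocol 4.6 and SAP section 4? | In Table 14.3.2.2.8? | Where else it appears |
|---|---|---|---|
| One eye, AE | No | Need not be | Table 14.2.4.3 under AE; AE listings |
| One eye, discomfort | No | Need not be | Table 14.2.4.3, category depending on how it was recorded; complaint and comfort summaries |
| Both eyes, AE | Yes | Yes | Table 14.2.4.3 under AE; disposition |
| Both eyes, discomfort | Yes | Only if the symptom was recorded as a TEAE | Table 14.2.4.3, probably under other if no AE was recorded; disposition; complaint and comfort summaries |

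Three routes can therefore be absent from the withdrawal table. The next question is whether the remaining outputs fill the gap.

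1. **By SOC/PT.** Table 14.2.4.3 counts removals for AE but carries no AE term. The action taken is recorded for each AE (SAP section 14), yet no table uses it to show the TEAEs that led to removal.
2. **Discomfort.** The three removal categories do not include it, although the protocol names it as a reason for removal.
3. **Subject-level total.** Removals are summarised by visit, and no cumulative count of subjects with an early removal for AE or discomfort is specified. The Unscheduled Visits rule in SAP section 9 brings unscheduled data into tables only when the scheduled data are missing. It is therefore unclear whether a removal between visits is tabulated.
4. **Disposition and exposure.** SAP section 10 counts anyone not discontinued from the study as a completer. Exposure runs to the last visualisation of a depot in either eye. A one-eye removal changes neither while the other depot remains visible.

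One conflict affects the first two rows of the table. The footnote in Protocol 4.5.7.9.1 (4, 8 and 10 Week Visits) exits a subject whose depot is removed for discomfort or an undesirable reaction, without separating one eye from both. SAP section 4 says that after a one-eye removal the other depot "will not be removed and the subject will be followed per the study schedule for safety", and Protocol 4.6 agrees with the SAP. Read literally, the footnote would turn those one-eye removals into exits, and any that were for a TEAE could then enter the withdrawal table.

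**The case against.** The strongest reply is that Table 14.3.2.2.8 counts exactly what its title says, and that treatment stops are reported elsewhere. Every removal has a recorded reason, tabulated by visit and arm and listed by right and left eye. Disposition gives reasons for discontinuation. Ocular complaints are tabulated with whether action was taken, and comfort scores are listed with any action to relieve discomfort. No efficacy inference is touched. All of this is correct, and it limits the point to the AE tables.

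A reader might infer two stronger things. The first is that stops for poor tolerability are under-counted in the report as a whole. The documents do not support that, because removals for AE are counted in Table 14.2.4.3 and exits in disposition. The second is that a subject who exits for discomfort with a normal slit lamp has no AE. That does not follow either:

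- The Note covers four queried complaints. It does not name pain or general discomfort, to which the general AE definition applies.
- Slit lamp findings are only an example of clinical sequelae.
- Tearing can qualify as the listed event epiphora, whose definition has no slit lamp condition.

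Such a subject may have no AE, and no more can be said. Nor is it certain that discomfort is filed under other, since an investigator who judged it an AE would record it as one.

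The replacement of early discontinuation by subject withdrawal in Version 2.0, made to match the CRF, is not an error. Neither term clearly covers a removal from one eye.

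What the reply leaves standing is that none of these outputs links a depot removal to an AE term in a table. A reader would have to match the AE and removal listings by hand.

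**Conclusion.** The point holds as a reporting gap in the AE tables. A one-eye removal for an AE need not appear in the AE outputs on stopping, and a bilateral removal for discomfort may not. No planned table shows by SOC/PT which TEAEs ended treatment, and discomfort has no removal category of its own.

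The documents give no removal rates, so the size cannot be estimated. For scale only, each 1% of subjects with such a removal would be 0.01 × 330 = 3.3 subjects on OTX-TP and 0.01 × 220 = 2.2 on placebo vehicle.

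The conclusion assumes that Protocol 4.6 and SAP section 4 govern one-eye removals. If the Protocol 4.5.7.9.1 footnote governs at the visits it covers, part of the one-eye gap closes. The discomfort gap and the missing removal category remain. The change is worth making because the data it mainly needs, action taken per AE and reason per removal, are already recorded.

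**What to change.** 1. Keep Table 14.3.2.2.8 as the clean count of withdrawals.
2. Add a table and listing of TEAEs leading to depot removal in either eye or to study exit, by SOC/PT and arm, derived from the recorded action taken and removal reason.
3. Add a cumulative subject-level count by arm of early removals for AE or discomfort, and state that removals at unscheduled visits are included. Show discomfort separately where the eCRF recorded it; the documents do not confirm that it did.
4. In the same derived table, count ocular complaints that led to removal or exit alongside the TEAEs. This leaves the complaint Note unchanged. The Note is protocol text that governs what investigators record, so changing it would be a protocol change and not only SAP wording.
5. Reconcile the Protocol 4.5.7.9.1 footnote with Protocol 4.6 and SAP section 4 on whether a one-eye removal leads to study exit, because that decides what enters the withdrawal table.

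The cost of items 2 to 4 is table shells, some programming and a higher reported count of treatment stops. Item 5 needs a clarification of the protocol text.

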Section 13 "Intracanalicular Depot Visualization by the Investigator" subsection	References have been changed from primary eye/secondary eye to right eye/left eye	Descriptions of Screening/Baseline assessment listings had previously been described using primary/secondary eye. However, since the CRFs collected these data with respect to right and left eyes and primary eye was not determined until Baseline Visit 2, these were changed to right eye/left eye.
Section 13 "Intracanalicular Depot Removal" subsection	References have been changed from primary eye/secondary eye to right eye/left eye	Descriptions of Screening/Baseline assessment listings had previously been described using primary/secondary eye. However, since the CRFs collected these data with respect to right and left eyes and primary eye was not determined until Baseline Visit 2, these were changed to right eye/left eye.
Section 14 "Primary Analysis" subsection	Typographical and grammatical errors have been corrected.	Originally in error.
Section 14.1.2 "Punctum Examination"	References have been changed from primary eye/secondary eye to right eye/left eye	Descriptions of Screening/Baseline assessment listings had previously been described using primary/secondary eye. However, since the CRFs collected these data with respect to right and left eyes and primary eye was not determined until Baseline Visit 2, these were changed to right eye/left eye.
Section 15 "AE Summaries" subsection	Typographical and grammatical errors have been corrected.	Originally in error.

Section 12 "Concomitant Medications" subsection	The population reference for the summary of ocular and non-ocular concomitant medications has been corrected from FAS to Safety Population	Originally in error.
Section 15 "AE Summaries" subsection	Terminology has been changed to "subject withdrawal"	To match CRF language.
Section 15 "AE Summaries" subsection	AEs of special interest were defined and a summary of AEs of special interest was added.	Sponsor request
Section 16 "Interim Analysis"	References to interim analysis were removed.	Sponsor determined that interim analysis was not needed.
Section 20 "Changes from Protocol- Stated Analyses"	A rationale was added for using FAS rather than ITT for primary analysis.	Further explanation was required.
Headers of Sections 23-25	References to interim analysis were removed.	Sponsor determined that interim analysis was not needed.
Titles of TLFs.	Typographical and grammatical errors have been corrected.	Originally in error.
Section 23 "Tables"	14.1.1, 14.1.6.3, 14.1.6.4 and 14.2.4.2 were added to the top line delivery	Sponsor's request
Section 23 "Tables"	A table for ocular TEAEs of special interest was added.	Sponsor's request
Section 24 "Listings"	A visit date listing was added.	Sponsor's request
Section 24 "Listings"	A rescue medication listing was added.	Sponsor's request
Section 25 "Figures"	Three figures were added.	Completing references from the SAP text

22. Tables

Tables that will be included in the topline delivery are shown in boldface font.

Table Number	Title	Population
Table 14.1.1	Subject Disposition	All Enrolled Subjects
Table 14.1.2	Major Protocol Deviations	Full Analysis Set
Table 14.1.3	Demographic and Baseline Characteristics	Full Analysis Set

Table Number	Title	Population
Table 14.1.4	Baseline Disease Characteristics	Full Analysis Set
Table 14.1.5.1	Non-Ocular Medical History	Safety Population
Table 14.1.5.2	Ocular Medical History	Safety Population
Table 14.1.6.1	Non-Ocular Concomitant Medications	Safety Population
Table 14.1.6.2	Ocular Concomitant Medications	Safety Population
Table 14.1.6.3	IOP-Lowering Ocular Medications	Safety Population
Table 14.1.6.4	Rescue Medication Use (IOP-Lowering Drops) by Visit	Full Analysis Set
Table 14.2.1.1	Mean Observed, Change, and Percent Change from Baseline in Primary Study Eye IOP by Time Point MCMC Analysis – Primary Time Points	Full Analysis Set
Table 14.2.1.2	Mean Observed, Change, and Percent Change from Baseline in Primary Study Eye IOP by Time Point MCMC Analysis – Non-Primary Time Points	Full Analysis Set
Table 14.2.1.3	Mean Observed, Change, and Percent Change from Baseline in Primary Study Eye IOP by Time Point Pattern Mixture Analysis	Full Analysis Set
Table 14.2.1.4	Mean Observed, Change, and Percent Change from Baseline in Primary Study Eye IOP by Time Point LOCF Analysis	Full Analysis Set
Table 14.2.1.5	Mean Observed, Change, and Percent Change from Baseline in Primary Study Eye IOP by Time Point BOCF Analysis	Full Analysis Set
Table 14.2.1.6	Mean Observed, Change, and Percent Change from Baseline in Primary Study Eye IOP by Time Point Observed Data Analysis	Full Analysis Set
Table 14.2.1.7	Mean Observed, Change, and Percent Change from Baseline in Primary Study Eye IOP by Time Point Observed Data Analysis	Per Protocol Population
Table 14.2.1.8	Mean Observed, Change, and Percent Change from Baseline in Secondary Study Eye IOP by Time Point Observed Data Analysis	Full Analysis Set
Table 14.2.1.9	Mean Observed, Change, and Percent Change from Baseline in Secondary Study Eye IOP by Time Point Observed Data Analysis	Per Protocol Population
Table 14.2.2.1	Mean Observed, Change, and Percent Change from Baseline in Primary Study Eye IOP by Time Point and Strata MCMC Analysis	Full Analysis Set
Table 14.2.4.1	Insertion Results and Ease of Insertion	Safety Population
Table 14.2.4.2	Summary of Replacements	Safety Population
Table 14.2.4.3	Removal of Intracanalicular Depot	Safety Population
Table 14.2.5	Ocular Complaints by Study Eye	Safety Population
Table 14.2.6	Investigator Visualization of Intracanalicular Depot	Safety Population
Table 14.2.7	Punctum Examination Results	Safety Population
Table 14.3.1	Study Treatment Exposure	Safety Population
Table 14.3.2.1	Overall Summary of Adverse Events	Safety Population
Table 14.3.2.2.1	Non-Ocular Treatment Emergent Adverse Events by System Organ Class and Preferred Term	Safety Population
Table 14.3.2.2.2	Ocular Treatment Emergent Adverse Events by System Organ Class and Preferred Term	Safety Population
Table 14.3.2.2.3	Primary Study Eye Ocular Treatment Emergent Adverse Events by System Organ Class and Preferred Term	Safety Population

Table Number	Title	Population
Table 14.3.2.2.4	Secondary Study Eye Ocular Treatment Emergent Adverse Events by System Organ Class and Preferred Term	Safety Population
Table 14.3.2.2.5	Treatment Related Ocular Treatment Emergent Adverse Events by System Organ Class and Preferred Term	Safety Population
Table 14.3.2.2.6	Treatment Related Non-Ocular Treatment Emergent Adverse Events by System Organ Class and Preferred Term	Safety Population
Table 14.3.2.2.7	Serious Adverse Events by System Organ Class and Preferred Term	Safety Population
Table 14.3.2.2.8	Treatment Emergent Adverse Events Leading to Subject Withdrawal by System Organ Class and Preferred Term	Safety Population
Table 14.3.2.2.9	Ocular Treatment Emergent Adverse Events of Special Interest by System Organ Class and Preferred Term	Safety Population
Table 14.3.2.3	Treatment Emergent Adverse Events by System Organ Class, Preferred Term, and Maximum Severity	Safety Population
Table 14.3.2.4	Non-Related Treatment Emergent Adverse Events by System Organ Class, Preferred Term, and Most Likely Cause	Safety Population
Table 14.3.3.1	Best Corrected Visual Acuity by Time Point and Eye	Safety Population
Table 14.3.3.2	Change from Baseline Category in Best Corrected Visual Acuity by Time Point and Eye	Safety Population
Table 14.3.4.1	Slit Lamp Biomicroscopy by Visit and Eye	Safety Population
Table 14.3.4.2	Shifts from Baseline in Slit Lamp Biomicroscopy by Visit and Eye	Safety Population
Table 14.3.5.1	Dilated Fundoscopy Examination by Visit and Eye	Safety Population
Table 14.3.5.2	Shifts from Screening to 12 Week Visit in Dilated Fundoscopy Examination by Visit and Eye	Safety Population
Table 14.3.6	Mean Observed and Change from Baseline in IOP by Time Point and Eye	Safety Population
Table 14.3.7.1	Slit Lamp Ocular Hyperemia by Visit and Eye	Safety Population
Table 14.3.7.2	Shifts from Baseline to Each Post-Baseline Visit in Ocular Hyperemia by Visit and Eye	Safety Population
Table 14.3.8	Mean Observed and Change from Baseline in Subject Ocular Comfort Assessment by Visit and Eye	Safety Population

23. Listings

Listing Number	Title	Population
Listing 16.1.7	Randomization Schedule	All Enrolled Subjects
Listing 16.2.1	Subject Disposition	All Enrolled Subjects
Listing 16.2.2.1	Protocol Deviations	All Randomized Subjects
Listing 16.2.2.2	Inclusion, Exclusion, and Procedural Exclusion Criteria	All Enrolled Subjects
Listing 16.2.2.3	Subjects Excluded from the Per Protocol Population	All Randomized Subjects
Listing 16.2.3	Visit Dates	All Randomized Subjects
Listing 16.2.4.1	Demographics	All Randomized Subjects
Listing 16.2.4.2	Baseline Characteristics: Current Diagnosis, Gonioscopy, Punctum Size, Cup to Disc Ratio, and Intraocular Pressure	Full Analysis Set
Listing 16.2.4.3	Pre-Treatment Perimetry	All Randomized Subjects

Listing Number	Title	Population
Listing 16.2.4.4	Pre-Treatment Pachymetry	All Randomized Subjects
Listing 16.2.4.5	Non-Ocular Medical History	Safety Population
Listing 16.2.4.6	Ocular Medical History	Safety Population
Listing 16.2.4.7	Prior and Concomitant Non-Ocular Medications	Safety Population
Listing 16.2.4.8	Prior and Concomitant Ocular Medications	Safety Population
Listing 16.2.4.9	Pregnancy Test Results	Safety Population
Listing 16.2.5.2	Insertion of Intracanalicular Depot	All Randomized Subjects
Listing 16.2.5.3	Investigator Intracanalicular Depot Visualization and Patency Check	Safety Population
Listing 16.2.5.4	Removal of Intracanalicular Depot	Safety Population
Listing 16.2.6.1	Intraocular Pressure	Safety Population
Listing 16.2.6.2	Ocular Complaints	Safety Population
Listing 16.2.8.1	Ocular Adverse Events	Safety Population
Listing 16.2.8.2	Serious Ocular Adverse Events	Safety Population
Listing 16.2.8.3	Ocular Adverse Events Leading to Subject Withdrawal	Safety Population
Listing 16.2.8.4	Non-Ocular Adverse Events	Safety Population
Listing 16.2.8.5	Serious Non-Ocular Adverse Events	Safety Population
Listing 16.2.8.6	Non-Ocular Adverse Events Leading to Subject Withdrawal	Safety Population
Listing 16.2.9.1	Best Corrected Visual Acuity (logMAR Scale)	Safety Population
Listing 16.2.9.2	Visual Acuity (logMAR) for Subjects Who Lost Three or More Lines	Safety Population
Listing 16.2.9.3	Slit Lamp Biomicroscopy	Safety Population
Listing 16.2.9.4	Dilated Fundus Examination and Cup to Disc Ratio	Safety Population
Listing 16.2.9.5	Punctum Examination Results	Safety Population
Listing 16.2.9.6	Punctum Size at Insertion	All Randomized Subjects
Listing 16.2.9.7	Slit Lamp Ocular Hyperemia and Ocular Comfort Assessment	Safety Population
Listing 16.2.9.8	Rescue (IOP-Lowering) Ocular Medications	Full Analysis Set

24. Figures

Figure Number	Title	Population
Figure 14.2.1	LSMeans for Primary Study Eye IOP by Time Point and Treatment (MCMC)	Full Analysis Set
Figure 14.2.2	LSMeans for Primary Study Eye IOP by Time Point and Treatment (MCMC)	Per Protocol Population
Figure 14.2.3	LSMeans Change from Baseline in Primary Study Eye IOP by Time Point and Treatment (MCMC)	Full Analysis Set
Figure 14.2.4	LSMeans Change from Baseline in Primary Study Eye IOP by Time Point and Treatment (MCMC)	Per Protocol Population
Figure 14.2.5	LSMeans Difference in Primary Study Eye IOP by Time Point (MCMC)	Full Analysis Set
Figure 14.2.6	LSMeans Difference in Primary Study Eye IOP by Time Point (MCMC)	Per Protocol Population
Figure 14.2.7	LSMeans for Primary Study Eye IOP by Time Point and Treatment (Observed Data)	Full Analysis Set
Figure 14.2.8	LSMeans for Primary Study Eye IOP by Time Point and Treatment (Observed Data)	Per Protocol Population
Figure 14.2.9	LSMeans Change from Baseline in Primary Study Eye IOP by Time Point and Treatment (Observed Data)	Full Analysis Set

Figure Number	Title	Population
Figure 14.2.10	LSMeans Change from Baseline in Primary Study Eye IOP by Time Point and Treatment (Observed Data)	Per Protocol Population
Figure 14.2.11	LSMeans Difference in Primary Study Eye IOP by Time Point (Observed Data)	Full Analysis Set
Figure 14.2.12	LSMeans Difference in Primary Study Eye IOP by Time Point (Observed Data)	Per Protocol Population
